Injury, poisoning and procedural complications	2 (13.3%)	1 (16.7%)	4 (66.7%)	2 (33.3%)	3 (50%)	1 (16.7%)	1 (16.7%)	6 (50%)	18 (37.5%)
Laceration	1 (6.7%)	0	2 (33.3%)	0	3 (50%)	1 (16.7%)	1 (16.7%)	3 (25%)	10 (20.8%)
Contusion	2 (13.3%)	0	1 (16.7%)	2 (33.3%)	0	0	0	1 (8.3%)	4 (8.3%)
Nervous system disorders	5 (33.3%)	1 (16.7%)	3 (50%)	2 (33.3%)	1 (16.7%)	3 (50%)	2 (33.3%)	3 (25%)	15 (31.3%)
Headache	5 (33.3%)	1 (16.7%)	1 (16.7%)	2 (33.3%)	0	2 (33.3%)	2 (33.3%)	3 (25%)	11 (22.9%)
Respiratory, thoracic and mediastinal disorders	6 (40%)	4 (66.7%)	0	1 (16.7%)	1 (16.7%)	1 (16.7%)	1 (16.7%)	4 (33.3%)	12 (25%)
Epistaxis	3 (20%)	1 (16.7%)	0	1 (16.7%)	1 (16.7%)	0	0	2 (16.7%)	5 (10.4%)
Cough	2 (13.3%)	2 (33.3%)	0	0	0	0	0	0	2 (4.2%)
Infections and infestations	5 (33.3%)	2 (33.3%)	5 (83.3%)	0	1 (16.7%)	0	1 (16.7%)	0	9 (18.8%)
Nasopharyngitis	2 (13.3%)	0	2 (33.3%)	0	1 (16.7%)	0	1 (16.7%)	0	4 (8.3%)
Investigations	1 (6.7%)	2 (33.3%)	2 (33.3%)	1 (16.7%)	1 (16.7%)	0	0	3 (25%)	9 (18.8%)
Blood creatine phosphokinase increased	1 (6.7%)	1 (16.7%)	0	0	1 (16.7%)	0	0	1 (8.3%)	3 (6.3%)

Table 1:Most Frequent (>5% Incidence) Treatment-Emergent Adverse Events - by Body System and Preferred Term: Part 1; Safety Analysis Set
(Study 64179375EDI1001)

AEs= adverse events; Plc=placebo

Note: Percentages calculated with the number of subjects in each group as denominator.

Note: Incidence is based on the number of subjects, not the number of events.

Reported dictionary version: MedDRA 19.1.

[TSFAE01P1.RTF] [JNJ-64179375\EDI1001\DBR_IA_SEQUESTERED\RE_IA_SEQUESTERED\PREPROD\TSFAE01P1.SAS] 25APR2017, 15:30

Table 2 shows all treatment-emergent bleeding adverse events selected using the Medical Dictionary for Regulatory Activities (MedDRA) standardized MedDRA queries (SMQ) term hemorrhage (excluding laboratory terms). In the placebo group, 46.7% of the subjects had 1 or more events compared with 72.9% for the combined JNJ-64179375 groups. This difference was mostly due to the increased incidence of treatment-emergent bleeding adverse events observed in the 2.125- (100%) and 2.5- (91.7%) mg/kg groups.

The most common bleeding adverse events observed were vessel puncture-site bruises JNJ-64179375, bleeding (placebo, 13.3%; 47.9%), gingival (placebo, 13.3%; JNJ-64179375, 20.8%), and epistaxis (placebo, 20%: JNJ-64179375, 10.4%). Most treatment-emergent bleeding adverse events were associated with mild trauma (ie, venipuncture, brushing teeth/gums, blowing nose) and all resolved. All were considered mild in intensity except for 6 events considered to be of moderate intensity (1 event of epistaxis at 1 mg/kg, 1 event of ecchymosis at 2.125 mg/kg, and 4 skin-bruising or hematoma events at 2.5 mg/kg). The criteria for moderate intensity were defined as an episode of epistaxis lasting more than 5 minutes or a skin bruise event with a maximum dimension of 10 cm or larger.

		JNJ-64179375										
	Plc	0.03 mg/kg	0.1 mg/kg	0.3 mg/kg	1.0 mg/kg	1.75 mg/kg	2.125 mg/kg	2.5 mg/kg	Active Total			
Subjects treated	15	6	6	6	6	6	6	12	48			
Subjects with 1 or more Bleeding AEs	7 (46.7%)	3 (50%)	5 (83.3%)	4 (66.7%)	2 (33.3%)	4 (66.7%)	6 (100%)	11 (91.7%)	35 (72.9%)			
Body System or Organ Class Dictionary-Derived Term												
General disorders and administration site conditions Vessel puncture site bruise Infusion site bruising Catheter site haemorrhage Infusion site haematoma Injection site bruising Vessel puncture site haematoma	3 (20%) 2 (13.3%) 1 (6.7%) 0 0 0 0	0 0 0 0 0 0 0	2 (33.3%) 2 (33.3%) 0 0 0 0 0 0 0	2 (33.3%) 2 (33.3%) 0 0 0 0 0 0 0	2 (33.3%) 2 (33.3%) 0 0 0 0 0 0	4 (66.7%) 4 (66.7%) 0 0 0 0 0 0	6 (100%) 6 (100%) 0 0 0 0 1 (16.7%)	8 (66.7%) 7 (58.3%) 2 (16.7%) 1 (8.3%) 1 (8.3%) 1 (8.3%) 0	24 (50%) 23 (47.9%) 2 (4.2%) 1 (2.1%) 1 (2.1%) 1 (2.1%) 1 (2.1%)			
Gastrointestinal disorders	2 (13.3%)	3 (50%)	1 (16.7%)	2 (33.3%)	0	0	2 (33.3%)	4 (33.3%)	12 (25%)			
Gingival bleeding	2 (13.3%)	2 (33.3%)	1 (16.7%)	2 (33.3%)	0	0	2 (33.3%)	3 (25%)	10 (20.8%)			
Haematochezia	0	0	0	0	0	0	0	1 (8.3%)	1 (2.1%)			
Mouth haemorrhage	0	1 (16.7%)	0	0	0	0	0	0	1 (2.1%)			
Injury, poisoning and procedural complications	2 (13.3%)	1 (16.7%)	1 (16.7%)	2 (33.3%)	0	0	0	2 (16.7%)	6 (12.5%)			
Contusion	2 (13.3%)	0	1 (16.7%)	2 (33.3%)	0	0	0	1 (8.3%)	4 (8.3%)			
Procedural haemorrhage	0	1 (16.7%)	0	0	0	0	0	0	1 (2.1%)			
Traumatic haemorrhage	0	0	0	0	0	0	0	1 (8.3%)	1 (2.1%)			
Respiratory, thoracic and mediastinal disorders	3 (20%)	1 (16.7%)	0	1 (16.7%)	1 (16.7%)	0	0	2 (16.7%)	5 (10.4%)			
Epistaxis	3 (20%)	1 (16.7%)	0	1 (16.7%)	1 (16.7%)	0	0	2 (16.7%)	5 (10.4%)			
Skin and subcutaneous tissue disorders	2 (13.3%)	0	0	0	0	0	1 (16.7%)	1 (8.3%)	2 (4.2%)			
Ecchymosis	1 (6.7%)	0	0	0	0	0	1 (16.7%)	0	1 (2.1%)			
Blood blister	1 (6.7%)	0	0	0	0	0	0	0	0			
Skin haemorrhage	0	0	0	0	0	0	0	1 (8.3%)	1 (2.1%)			
Investigations	0	1 (16.7%)	1 (16.7%)	0	0	0	0	1 (8.3%)	3 (6.3%)			
Blood urine present	0	1 (16.7%)	1 (16.7%)	0	0	0	0	1 (8.3%)	3 (6.3%)			
Ear and labyrinth disorders	0	0	0	0	0	0	1 (16.7%)	0	1 (2.1%)			
Ear haemorrhage	0	0	0	0	0	0	1 (16.7%)	0	1 (2.1%)			

Table 2: Treatment-Emergent Bleeding Adverse Events - by Body System and Preferred Term: Part 1; Safety Analysis Set (Study 64179375EDI1001)

AE=adverse event; Plc=placebo

Note: Percentages calculated with the number of subjects in each group as denominator.

Note: Incidence is based on the number of subjects, not the number of events.

Reported dictionary version: SMQ19.1, HAEMORRHAGE TERMS (EXCL LABORATORY TERMS) (SMQ)

[TSFAE02P1.RTF] [JNJ-64179375\EDI1001\DBR_IA_SEQUESTERED\RE_IA_SEQUESTERED\PREPROD\TSFAE02P1.SAS] 25APR2017, 15:30

Clinical Laboratory, Vital Signs, and ECG Assessments

Clinical safety laboratory tests (clinical chemistry, hematology, coagulation, and urinalysis), vital signs, and ECGs were collected at specified times before and after study drug dosing.

There were no apparent group-mean trends or dose-related effects in these assessments with JNJ-64179375, with the exception of dose-related increases in PT, aPTT, and TT levels consistent with the mechanism of action of JNJ-64179375 (see Section 1.1.2.2.4, Pharmacodynamics). Individual ECGs did not show any clinically significant changes from baseline; no subject had a QT corrected according to Fridericia's formula (QTcF) >450 msec or an increase from baseline in QTcF >30 msec.

1.1.2.2.3. Pharmacokinetics

The results presented below are based on preliminary bioanalytical data and nominal sampling times from the subjects who received at least 1 dose of JNJ-64179375 in Part 1. Plasma samples were analyzed to determine concentrations of JNJ-64179375 using a validated, selective, and sensitive immunoassay method (lower limit of quantification 0.01 μ g/mL). Interim preliminary PK results were determined using noncompartmental methods and are summarized in Table 3.

		(8 8/	,			
	JNJ-64179375	C _{max}	T _{max} ^a	AUC _{inf}	CL	Vz	t _{1/2}
Cohort	mg/kg IV	μg/mL	h	day*µg/mL	mL/day/kg	mL/kg	day
1	0.03	0.707 (0.196)	1 (0.5-1)	15.4 (3.87)	2.07 (0.628)	73.3 (21.8)	24.7 (3.6)
2	0.1	2.15 (0.183)	1 (0.5-8)	47.2 (6.74)	2.16 (0.361)	76.3 (5.67)	24.8 (3.2)
3	0.3	6.86 (1.30)	1 (0.5-4)	145 (22.3)	2.11 (0.286)	78.8 (19.1)	26.0 (5.3)
4	1	28.4 (3.90)	1 (0.5-4)	514 (71.3)	1.98 (0.285)	83.0 (11.5)	29.2 (3.1)
5+6	2.5	58.0 (12.7)	2.5 (0.5-8)	1266 (266)	2.06 (0.487)	80.5 (12.4)	27.8 (5.2)
7	1.75	44.3 (8.90)	2.5 (0.5-4)	813 (124)	2.20 (0.328)	68.7 (9.64)	21.8 (2.1)
8	2 125	42 9 (3 62)	1(0.5-4)	970 (209)	2 28 (0 499)	73 5 (15 3)	23 2 (6 9)

Table 3:Mean (±SD) Pharmacokinetic Parameters of JNJ-64179375 Following a Single 30-minuteIV Infusion (0.03 to 2.5 mg/kg, Part 1) in Healthy Male Subjects

AUC_{inf}=area under the concentration curve from zero to infinity; CL= total clearance of drug after IV administration; C_{max} = maximum concentration during a dosing interval; h=hour; IV=intravenous; SD=standard deviation; $t_{1/2}$ =terminal half-life; T_{max} =time to reach the maximum observed plasma concentration; Vz=apparent volume of distribution in the terminal phase

^aData presented as Median (Minimum-Maximum)

The median time to reach the maximum observed plasma concentration (T_{max}) was 1 to 2.5 hours postdose. The mean C_{max} and AUC_{inf} increased in an approximately dose-proportional manner. The mean $t_{1/2}$ ranged from approximately 21.8 to 29.2 days.

1.1.2.2.4. Pharmacodynamics

Prothrombin time, aPTT, and TT demonstrated dose-dependent increases whether measured locally or at a central specialty laboratory, with TT being the most sensitive test and PT the least sensitive test. A plot of mean ratio to baseline for TT from the central specialty laboratory is provided in Figure 1. For TT, the 2 highest dose groups showed similar prolongations for the early timepoints (an approximately 7-fold increase) as some subjects in both groups exceeded the laboratory upper reporting limit of 120 seconds. At 14 days, the prolongation in TT was about 5-fold for the highest dose group. At the 0.3-mg/kg dose level, the peak prolongation in TT was

approximately 2.7-fold and it was approximately 1.7-fold at 14 days. For aPTT, the assay upper reporting limit was not approached for any subject but the maximum prolongation appears to be an approximately 1.6-fold increase from baseline for each of the 3 highest dose groups. For PT, the maximum-fold increase was approximately 1.3-fold at the highest dose. These data are consistent with the in-vitro data and with the mechanism of action of JNJ-64179375. Local laboratory results demonstrated a similar pattern.

1.1.2.2.5. Overall Summary

In this single-ascending dose (SAD), randomized, double-blind, placebo-controlled study in healthy male subjects (Part 1), JNJ-64179375 was generally well tolerated at all doses. All observed bleeding events were of mild or moderate intensity, mostly related to local trauma (eg, venipuncture, brushing teeth, blowing nose), and none were severe or serious. At the 2 highest doses (2.125 and 2.5 mg/kg), an increased frequency (and severity at 2.5 mg/kg) of bleeding events was observed compared with placebo.

With the exception of the bleeding adverse events, there was no evidence of dose-dependent adverse events over the studied dose range. As hypersensitivity reactions have been observed with the administration of monoclonal antibodies, infusion or allergic reactions were closely monitored for this study. One subject in the 2.5-mg/kg cohort developed mild urticaria that started prior to receiving the study drug. The urticaria spread and was assessed as moderate in severity at approximately 4 hours postdose. The urticaria resolved spontaneously 24 hours later and was considered doubtfully related to the study drug.

JNJ-64179375 administered as an IV infusion exhibited a favorable PK profile in healthy subjects, and the observed PK parameters were close to those predicted based on the animal PK data. Mean C_{max} and AUC_{inf} values increased in an approximately dose-proportional manner in the studied dose range. Mean $t_{1/2}$ ranging from 21.8 to 29.2 days is consistent with the expected $t_{1/2}$ of human IgG4. Importantly, variations of the PK concentration and parameters (C_{max} and AUC_{inf}) of JNJ-64179375 were low, indicating PK predictability.

Consistent with the nonclinical findings, JNJ-64179375 produced a dose-dependent prolongation of the coagulation parameters (PT, aPTT, and TT) over the studied dose range. Based on fold-changes from baseline observed in this study, TT was the most sensitive assay for JNJ-64179375, which is consistent with its mechanism of action and direct effect on thrombin-mediated clot formation. The effect-time curves for all coagulation parameters seemed parallel to the plasma drug concentration-time curves of JNJ-64179375 with no apparent lag time.

1.1.2.3. Parts 2 and 3

Parts 2 and 3 of the study (1 single cohort in each part) had also completed dosing as of 21 April 2017. A blinded data review as of 02 May 2017 is briefly summarized below; however, this data was not included in the unblinded interim analysis as it was not available until after the cutoff date. Eight subjects were dosed intravenously with 1.0 mg/kg of JNJ-64179375 in Part 2 followed by either placebo (n=2) or 50 IU/kg of the 4-factor PCC Confidex[®] (n=6). Confidex did not appear to reverse the effects of JNJ-64179375 on either aPTT or TT. In Part 3, 8 subjects were dosed subcutaneously with either 1.0 mg/kg of JNJ-64179375 (n=6) or placebo (n=2). The PK data showed the expected delay to peak drug levels. For both cohorts, the bleeding adverse events were mostly mild skin-site events as observed in Part 1. One moderate intensity epistaxis bleeding event was reported in Part 2.

In the nonclinical studies, 4-factor PCC and activated PCC were able to normalize rat-tail bleeding times after the administration of JNJ-64179375 but did not reverse TT or aPTT prolongation (data on file). Therefore, the lack of reversal of TT and aPTT with 4-factor PCC in Part 2 of the Phase 1 study was not unexpected and likely reflects the insensitivity of these coagulation assays for measuring the potential hemostatic effects of PCC administration.

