11.9. Safety Analyses

All safety data will be fully listed. The reporting of the safety data of all subjects receiving at least 1 active dose of JNJ-64179375 or apixaban will include the incidence and type of adverse events, plus absolute values and changes in blood pressure (systolic and diastolic), HR, clinical laboratory data, and physical examinations from predose to the final postdose time point.

Adverse Events

The verbatim terms used in the eCRF by investigators to identify adverse events will be coded using the MedDRA. Treatment-emergent adverse events are adverse events with onset during the treatment phase or that are a consequence of a preexisting condition that has worsened since baseline. All reported adverse events will be included in the analysis. For each adverse event, the percentage of subjects who experience at least 1 occurrence of the given event will be summarized by treatment group. In addition, comparisons between treatment groups will be provided if appropriate.

Summaries, listings, datasets, or subject narratives may be provided, as appropriate, for those subjects who die, who discontinue treatment due to an adverse event, or who experience a severe or a serious adverse event.

Based on the mechanism of action of JNJ-64179375 and given that it is a monoclonal antibody, adverse events of special interest will include bleeding events, infusion reactions, hypersensitivity reactions, and wound or joint complications as described in Section 9.7.2, Adverse Events of Special Interest. Subjects with adverse events of special interest may be counted or listed using MedDRA SMQs (eg, hemorrhage excluding laboratory terms SMQ). All suspected symptomatic efficacy (thrombotic) events will also be captured as adverse events of special interest.

Clinical Laboratory Tests

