The primary risk with any anticoagulant drug is the potential for bleeding events, and because JNJ-64179375 is a monoclonal antibody, infusion and hypersensitivity reactions could also be potentially observed. Based on the nonclinical evaluations of JNJ-64179375, the risk for these events is anticipated to be low (ie, all planned doses are below those shown to statistically significantly increase bleeding risk) and no cytokine release or allergic reactions have been observed in animals. In addition, subjects in the first-in-human SAD study did not experience any infusion or hypersensitivity reactions. A bleeding signal was detected at the 2.125- and 2.5-mg/kg doses in healthy male subjects. This signal consisted primarily of increased local bruising at the venipuncture and infusion sites in subjects who received JNJ-64179375 compared with placebo. The starting dose of 0.3 mg/kg in Part 1 is approximately one-seventh of this dose and was well tolerated in the SAD study. The highest planned dose (1.2 mg/kg) in Part 1 of this study is approximately 50% of the 2.125-mg/kg dose and will only be studied if lower doses are tolerated. Subjects in this study will be carefully observed for both bleeding events and infusion or hypersensitivity reactions throughout the duration of the study and management strategies for each type of event are outlined in the protocol (see Section 9.7.2.1.2, Approach to Subjects With a Bleeding Event and Section 9.7.2.2, Infusion or Hypersensitivity Reactions, respectively).

Venography assessments will be used to evaluate for the presence of DVT. The x-ray used in the imaging exposes the body to a small dose of ionizing radiation. The risks of radiation exposure may be tied to the number of x-rays and x-ray treatments a person has had over their lifetime.

Given that all of the subjects in this study will be \geq 50 years of age, the incremental risk of this radiation exposure is considered small. X-rays are the oldest and most frequently used form of medical imaging. Other risks associated with venography assessments include pain, infection, and/or bleeding at the site of venous access and the risks from contrast medium administration (ie, allergy, nephrotoxicity, and/or possible irritation of the venous system leading to the development of DVT). In previous studies, venography assessments have been well tolerated and do provide clinically useful information about the presence or absence of DVT following surgery.²⁶

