6.4. Adverse Events

The verbatim terms used in the CRF by investigators to identify adverse events will be coded using the Medical Dictionary for Regulatory Activities (MedDRA). Any AE occurring at or after the initial administration of study agent through the day of last dose to up to last contact date is considered to be treatment emergent. If the event occurs on the day of the initial administration of study agent, and either event time or time of administration are missing, then the event will be assumed to be treatment emergent. If the event date is recorded as partial or completely missing, then the event will be considered to be treatment emergent unless it is known to be prior to the first administration of study agent based on partial onset date or resolution date. All reported treatment-emergent adverse events will be included in the analysis. For each adverse event, the number and percentage of subjects who experience at least 1 occurrence of the given event will be summarized by treatment group. In addition, comparisons between treatment groups will be provided if appropriate.

Summary tables will be provided for:

- All AEs and TEAEs
- All Serious AEs (SAEs) and TESAEs
- AEs leading to discontinuation of study agent/termination of study participation
- TEAEs by severity
- TEAEs by relationship to study agent

In addition to the summary tables, listings will be provided for subjects who:

- Had SAEs
- Had AEs leading to discontinuation of study agent

Incidence of other treatment-emergent adverse events of special interest will be summarized.

As per protocol, adverse events of special interest include bleeding events, infusion reactions, hypersensitivity reactions, and wound or joint complications. All suspected symptomatic efficacy(thrombotic) events will also be captured as adverse events of special interest. Subjects with adverse events of special interest may be counted or listed using MedDRA SMQs (eg, hemorrhage excluding laboratory terms SMQ).

The following maps the location in eCRF of adverse events of special interest

Adverse events of special interest	eCRF Form names(s)	Comments
Specify AE special interest type	Adverse Events/Serious AEs	

Deaths will be displayed by actual treatment received. Frequencies for the following parameters will be included in the summary table:

- Number of subjects who died
- Cause of death
- Relationship to study agent (yes/no)

A listing of subjects who died will be provided.

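### SAP Section 6.4 omits the protocol's worsened-since-baseline limb, so an adverse event recorded once with pre-dose onset that worsens after dosing drops out of the Part 1 treatment-emergent summaries

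*Protocol*

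**What the plan says.** Protocol Section 11.9 gives two routes to treatment-emergent status. The first is onset during the treatment phase. The second covers events "or that are a consequence of a preexisting condition that has worsened since baseline". The same section adds: "All reported adverse events will be included in the analysis".

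SAP Section 6.4 has one route: "Any AE occurring at or after the initial administration of study agent through the day of last dose to up to last contact date". An event with a partial or missing date is presumed treatment-emergent "unless it is known to be prior to the first administration of study agent based on partial onset date or resolution date". The inclusion sentence is narrower than the protocol's: "All reported treatment-emergent adverse events will be included in the analysis". On special-interest events the SAP says: "Incidence of other treatment-emergent adverse events of special interest will be summarized". The tables by severity and by relationship to study agent are also limited to treatment-emergent events. Nothing in the SAP addresses an event that precedes dosing and then worsens. The SAP states that it is based on this protocol amendment and gives no reason for the difference.

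The protocol's Phase 1 background (Section 1.1.2.2.5) describes an event of that kind, in a subject with "mild urticaria that started prior to receiving the study drug. The urticaria spread and was assessed as moderate in severity at approximately 4 hours" after dosing.

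**The concern.** The two documents can classify the same event differently, and the SAP is the one that will be programmed. The setting makes the pattern plausible. Adverse events are collected from signed consent (protocol Section 9.7.1), screening may take place before or after the operation (Section 9.1.2), and first dose comes 12 to 24 hours after wound closure (Section 6). There is therefore a postoperative interval in which events can be recorded before any study drug is given.

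The summaries affected describe how severe events were, whether they were judged related, and how often special-interest events occurred. Part 1's primary objective is safety and tolerability by dose level, and this SAP produces the Part 1 topline report. Hypersensitivity and infusion reactions are the clearest case, because the SAP gives them no separate analysis outside the adverse-event section.

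**Working it through.** No figure in the plan is at stake, so the check is a comparison of rules.

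1. **Does the SAP rule work as an onset test?** It says occurring, not starting, so this is an inference. Two things support it. The rule for partial or missing dates asks whether the event is known to precede first administration. SAP Section 2.8 handles one onset and one resolution date and time per event and has no date of worsening. A single record with a full pre-dose onset date therefore has nothing that would place it at or after first dose.

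2. **Apply both rules to one pattern.** Take an event that is mild before dosing, moderate after dosing, and held as one record with its pre-dose onset.
   - Protocol Section 11.9: treatment-emergent, through the worsening limb.
   - SAP Section 6.4: not treatment-emergent.

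   The Phase 1 urticaria in protocol Section 1.1.2.2.5 has this course, and Section 9.7.2.2 lists urticaria among its examples of infusion or hypersensitivity reactions. It serves only as an illustration. It comes from a different study, and the protocol does not say how it was recorded.

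3. **Trace the event through the SAP outputs.**
   - Missing: treatment-emergent events overall, by severity and by relationship, and treatment-emergent special-interest events.
   - Still present: the all-AE table, the all-SAE table if serious, and the discontinuation table if it led to stopping study agent or leaving the study.
   - Not governed by the flag: bleeding endpoints, which have their own eCRF form and observation periods (SAP Sections 6.1.1 and 6.1.2), and wound or joint complications, which have their own eCRF page and table on the safety set (SAP Section 6.3, Table 6).

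4. **Does the definition of an adverse event close the gap?** Protocol Section 12.1.1 counts aggravation of a baseline condition as an adverse event, and Section 9.7 requires clinically relevant changes to be recorded. If the site opens a new record at the date of worsening, that record has post-dose onset and the SAP captures it. Neither document tells sites to do so when an event record is already open. The gap is therefore confined to events held as one record with pre-dose onset.

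**The case against.** The strongest reply is that this is a wording mismatch with little consequence. Aggravation is already an adverse event by definition, so a properly recorded worsening would carry a post-dose date. The SAP also looks forward further than the protocol: its window runs to last contact, whereas the protocol refers to the treatment phase, so in that respect it captures more. The event would still appear in the all-AE table, and protocol Section 11.9 has all safety data listed. These points stand and keep the issue small. They do not remove it, because capture depends on a recording practice that neither document specifies.

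Four stronger readings are tempting, and the documents do not support them.

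- A reader might infer that postoperative oozing, hematoma or drainage would be lost and that dose decisions would suffer. Bleeding and wound events have outputs that do not depend on the flag. The suggested escalation criteria in SAP Section 3.1.1 rest on bleeding endpoints, with the major VTE composite as a further guide. Part 2 dose selection considers all the data with a focus on any bleeding and total VTE.
- A reader might infer that the rule hides harm from JNJ-64179375 specifically. It applies alike to every arm, and the comparator is also an anticoagulant, so no direction of bias is shown.
- A reader might count the urticaria as a case on active drug. Section 1.1.2.2.5 gives only the 2.5-mg/kg cohort, and Phase 1 cohorts included placebo subjects, so treatment received is not stated.
- A reader might infer that protocol Section 16.1 is wrong to say that "subjects in the first-in-human SAD study did not experience any infusion or hypersensitivity reactions". The urticaria began before dosing and was judged doubtfully related, which is compatible with that sentence.

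**Conclusion.** The mismatch is real. SAP Section 6.4 is narrower than protocol Section 11.9 on worsening, without explanation, and should be aligned. The consequence is limited to the Part 1 treatment-emergent summaries, chiefly those by severity, by relationship and for special-interest events such as hypersensitivity reactions. An effect on the bleeding endpoints, dose escalation or Part 2 dose selection is not shown.

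The size cannot be given as a number. The documents report neither how often events begin between consent and first dose nor how often those worsen afterwards.

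The conclusion rests on two assumptions: that the SAP's single route operates on the recorded onset date, and that at least some sites keep one record for an event that worsens. It concerns Part 1 only. The Part 2 SAP is a separate document and was not available for review.

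**What to change.** In SAP Section 6.4, add to the treatment-emergent definition events with onset before first administration that worsen at or after it, and tabulate them at their post-dose severity. Keep the existing follow-up window to last contact. State how worsening is recorded and dated, for example as a new adverse-event record opened on the date of worsening, and put the same instruction in the eCRF guidance. Protocol Section 11.9 does not define worsening operationally, so the SAP should say what counts, such as an increase in severity grade. Carry the same definition into the Part 2 SAP.

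The cost is a sentence or two in the SAP, a short eCRF instruction and minor programming. No visits, samples or subjects are added.
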